## **1 INTRODUCTION**

The objective of the KD025-213 study is to evaluate the efficacy and safety of KD025, at dose levels of 200mg QD and 200mg BID, in subjects with cGVHD who have previously been treated with two to five prior lines of systemic therapy.

This Statistical Analysis Plan (SAP) describes data-handling and statistical procedures to be used for the analysis and reporting of efficacy and safety data collected under Study KD025-213 and presented in the clinical study report (CSR). This SAP has been developed and finalized prior to locking the clinical database. Pharmacokinetic (PK) and Pharmacodynamic (PD) analyses will be described in separate documents.

The SAP was written in accordance with the recommendations outlined in the International Conference on Harmonisation (ICH) E9 Guideline entitled “Guidance for Industry: Statistical Principles for Clinical Trials” and the most recent ICH-E3 Guideline, entitled “Guidance for Industry: Structure and Content of Clinical Study Reports.”

## **2 STUDY SUMMARY**

### **2.1 Study Objectives**

Primary objective:

- To evaluate the efficacy (overall response rate (ORR) as assessed by investigator) and safety of KD025, at dose levels of 200mg QD and 200mg BID, in subjects with cGVHD who have previously been treated with two to five prior lines of systemic therapy.

Secondary objectives:

- Duration of response (DOR)
- Changes in the Lee Symptom Scale Score
- Response by organ system
- Time to response
- Time to next treatment (TTNT)
- Percentage of subjects who have a best response of partial response (PR) and percentage of subjects who have a best response of complete response (CR)
- Change in corticosteroid dose
- Change in calcineurin inhibitor dose
- Failure-free-survival (FFS)

- Overall survival (OS)
- Change in cGVHD severity using the Clinician-Reported Global cGVHD Activity Assessment
- Change in symptom activity using the cGVHD Activity Assessment Patient Self-Report
- PK of KD025 in subjects with cGVHD

Exploratory Objectives:

- To evaluate changes in the PROMIS Global Health sub-scores for physical and mental functioning
- To evaluate ORR using sponsor assessments of overall response
- To evaluate changes in relevant biomarkers after KD025 administration

## 2.2 Study Design

KD025-213 is a Phase 2, open label, randomized, multicenter study in subjects with cGVHD who have previously been treated with two to five prior lines of systemic therapy. The study schematic is shown below in [Figure 1](#). Approximately 126 subjects with active cGVHD will be randomized (1:1) to receive treatment with one of two KD025 regimens:

[figure not shown]
- Arm A: KD025 200mg QD
- Arm B: KD025 200mg BID

Subjects may receive treatment in 28-day treatment cycles until clinically significant progression of cGVHD (defined as progression requiring addition of new systemic therapy for cGVHD), histologic recurrence of underlying malignancy, unacceptable toxicity, Investigator decision, subject preference / withdrawal of consent, loss to follow-up, sponsor decision, or death (whichever occurs first). Subjects who have not achieved a response after 12 cycles of KD025 should be withdrawn if in the Investigator's judgment there is no evidence of clinical benefit.

Subjects will undergo evaluations as outlined in the Schedule of Assessments (see Table 12 in KD025-213 Study Protocol).

The primary endpoint is the ORR with responses as defined by the 2014 National Institute of Health (NIH) Consensus Development Project on clinical trials in cGVHD.

**Figure 1 KD025-213 Study Schema**

## 2.3 Number of Subjects

Approximately 126 subjects will be enrolled.

## 2.4 Randomization

Subjects will be randomized to either Arm A (200mg QD) or Arm B (200mg BID) with 1:1 ratio and block size 4. Randomization will be stratified according to:

- Prior ibrutinib therapy (Yes / No)
- Severe cGVHD (yes/no) where severe cGVHD is defined as at least one organ with a score of 3, or a lung score of 2 or 3

## 2.5 Replacements

Randomized subjects withdrawn from the study before receiving any study drug will be replaced.

### 3 STATISTICAL METHODS

#### Three analyses are planned:

- An interim analysis (IA) will be conducted approximately 2 months after 126 subjects have been enrolled into the mITT population. A nominal 1-sided alpha of 0.0025 will be spent, but there will be no early study termination for efficacy.
- The primary analysis (PA) will be conducted approximately 6 months after 126 subjects have been enrolled into the mITT population, with 1-sided alpha 0.0225 (or 0.025 if the ORRs of both arms are significant at interim).
- A follow-up analysis will be conducted approximately 12 months after 126 subjects have been enrolled into the mITT population.

Alpha will only be allocated to the primary endpoint, ORR.

#### 3.1 Sample Size Justification

The sample size for KD025-213 is based upon the following considerations:

[figure not shown]
- The primary efficacy objective is to demonstrate an ORR > 30%, i.e. that the lower bound of the CI of ORR is greater than 30%
- There is an interim analysis with .0025 1-sided alpha spending
- A true ORR of 55% is assumed based upon data from an ongoing study of KD025 (KD025-208) in patients with cGVHD after 1-3 prior lines of systemic therapy. In the KD025-208 study, the ORR was 65% in Cohort 1 (200mg QD), 63% in Cohort 2 (200mg BID) and 52% in Cohort 3 (400mg QD) as of 13-September, 2018.
- A 10% dropout rate is assumed based upon data from the ongoing KD025-208 study (estimated ~6% dropout rate in KD025 208). Dropouts are defined as a subjects discontinuing KD025 treatment prior to any response assessment, due to reasons other than an AE related to study drug or cGVHD progression

For a single arm, assuming a true ORR of 55%, dropout rate of 10%, power 90%, and 2-side alpha of .045 to demonstrate ORR > 30%, the sample size is calculated to be 63.

### 3.2 Multiplicity Adjustment

Since the study has two KD025 treatment arms, the Hochberg procedure will be used for multiplicity adjustment for the primary endpoint as shown in [Figure 2](#).

**Figure 2 ORR Multiplicity Adjustment**

Simulations were conducted with various hypothetical ORR scenarios for two arms of 63 subjects, by using the Hochberg procedure for multiplicity adjustment; results (10000 runs per setting) are presented in [Table 1](#).

Only descriptive statistics will be provided for all secondary and exploratory endpoints, without multiplicity adjustment.

### 3.3 Sample Size Adjustment

If during the course of the current study the dropout rate is observed to exceed 10%, the sample size may be adjusted to maintain overall power e.g., to approximately 85 subjects per arm if the dropout rate reaches 15%.

### 3.4 Analysis Populations

**mITT:** The primary population for efficacy analyses will be a modified Intent to treat (mITT) population defined as all randomized subjects who receive at least one dose of study medication.

**Table 1: Power for various hypothetic ORRs**

Table 1a: IA Power (1-sided alpha 0.0025)*						
For both arms to be statistically significant						
		Arm 1 ORR (%)				
		40	45	50	55	60
Arm 2 ORR (%)	40	< 1	< 1	< 1	< 1	< 1
	45	-	< 1	1	2	3
	50	-	-	2	6	9
	55	-	-	-	12	22
	60	-	-	-	-	37
For at least one arm to be statistically significant						
		Arm 1 ORR (%)				
		40	45	50	55	60
Arm 2 ORR (%)	40	1	3	10	28	51
	45	-	5	12	29	53
	50	-	-	20	35	57
	55	-	-	-	65	65
	60	-	-	-	-	77
Table 1b: PA Power (1-sided alpha 0.0225)*						
		Arm 1 ORR (%)				
		40	45	50	55	60
Arm 2 ORR (%)	40	20	39	64	84	95
	45	-	52	72	89	97
	50	-	-	83	93	98
	55	-	-	-	97	99
	60	-	-	-	-	100

IA = Interim Analysis; PA = Primary Analysis  
\* Power estimated based upon 10,000 simulations for each cell

The mITT population will be used for tables of demography, baseline characteristics and efficacy.

**Responder:** The responder population is defined as subjects in the mITT population that achieved a partial or complete response at any post-baseline response assessment.

**Nonresponder:** The nonresponder population is defined as anyone in mITT population that is not a responder.

The responder and nonresponder populations will be used for some subgroup analyses.

**Safety:** The safety population is defined as all randomized subjects who receive at least one dose of study medication. In this study, safety population is equivalent to mITT population.

### **3.5 Protocol Deviations**

All protocol deviations will be identified and classified as major or minor (as defined below) before the clinical database lock, and will be presented in a listing.

**Major Deviation:** Protocol deviation that may impact the accuracy, and/or reliability of the study data or that may impact subject rights, safety or well-being.

**Minor Deviation:** Protocol deviation that does not impact the accuracy, and/or reliability of the study data or subject rights, safety or well-being.

**Serious non-compliance:** Serious noncompliance presents a significant risk to the safety of study patients or significantly affects the scientific value of the reported results of the study. This classification may include fraud, scientific misconduct and serious breaches of ethical conduct. Persistent clinical investigator site noncompliance, even if not serious, is also considered within this definition.

### **3.6 Subject Disposition**

A disposition of all enrolled subjects will be summarized. The number of subjects discontinuing from the study and the primary reason for discontinuation will be summarized.

### **3.7 Demographics and Baseline Characteristics**

#### **3.7.1 Demographics**

Subject demographics and baseline characteristics will be summarized for the mITT population. Descriptive statistics will be provided for age, height, weight, and body mass index (BMI). Frequencies and percentages will be tabulated for sex, race, and ethnicity.

#### **3.7.2 Medical History**

Medical history will be summarized by primary system organ class (SOC) and preferred term (PT). Medical history will be coded using Medical Dictionary for Regulatory Activities (MedDRA, Version 20.1 or higher) terminology.

#### **3.7.3 GVHD and Transplant History**

The GVHD history will be summarized including transplant history and prior therapies.

Transplant history will be summarized for:

- Indication for transplant
- Stem cell type (bone marrow, peripheral blood, cord blood)
- Donor source (related, unrelated)
- Conditioning regimen (myeloablative, nonmyeloablative)
- Donor age
- Donor gender
- Donor-recipient gender mismatch
- Donor-recipient CMV serostatus

The baseline characteristics of GVHD will be summarized for:

- GVHD prophylaxis
- Prior aGVHD
- Time from transplant to cGVHD diagnosis
- Time from cGVHD diagnosis to enrollment
- Time from transplant to enrollment
- cGVHD severity: mild / moderate / severe

#### Prior Therapies

- Number of prior lines of systemic cGVHD therapy
- Ongoing systemic cGVHD therapies at baseline

- Listing of all non-systemic cGVHD therapies

Organ Involvement

- Number of organs involved at baseline
- Organ involvement at baseline, Including
  - baseline skin NIH score and skin feature score
  - eye NIH score
  - NIH modified oral mucosa rating scale (OMRS) score
  - esophagus NIH score
  - upper GI NIH score
  - lower GI NIH score
  - alanine transaminase (ALT), alkaline phosphatase (ALP), total bilirubin
  - lung NIH score and FEV1 (% predicted)
  - joint/fascia NIH score and P-ROM score
  - global severity rating

### **3.7.4 Other Baseline Characteristics**

Other baseline values including Karnofsky Performance Scale (KPS), child bearing potential, will also be summarized.

## **3.8 Efficacy Endpoints and Analyses**

### **3.8.1 Primary Efficacy Endpoint: ORR**

The primary efficacy endpoint is the overall response rate, with response status as assessed by investigators based upon the 2014 NIH Consensus Development Project on Clinical Trials in cGVHD (see Protocol Appendix F: cGVHD Response Assessment).

Response is assessed using individual scores from ten systems (Skin, Eyes, Mouth, Esophagus, Upper GI, Lower GI, Liver, Lungs, Joints and Fascia and Global Severity Rating (GSR)). Response is assessed with respect to the baseline (Cycle 1, Day 1 (C1D1)) cGVHD assessment. The overall response at each assessment time point will be categorized as Complete Response (CR), Partial Response (PR), or Lack of Response (LR), where LR includes the response status of unchanged, mixed, or progression as defined in [Table 2](#).

The ORR is defined as the proportion of subjects with a best response meeting the overall response criteria assessment of CR or PR at any post-baseline response assessment.

If a treated subject is lost to follow up without response assessment, this subject will be counted as a non-responder. Any response on and after new systemic cGVHD treatment will be censored as non-response.

Point estimates, various confidence intervals (Clopper-Pearson (exact) method) listed in Figure 2, and raw and Hochberg adjusted p-values corresponding to the null hypothesis of  $ORR \leq 30\%$  vs alternative hypothesis of  $ORR > 30\%$  by treatment arms will be reported.

The number and percentage of subjects who have a best response of PR and number and percentage of subjects who have a best response of CR will also be reported.

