5.8.1 Corticosteroids

Corticosteroid dose data will be collected throughout the study. Corticosteroids may be tapered at the discretion of the Investigator after ≥ 2 weeks of belumosudil administration.

Transient increases in corticosteroid dosing (not exceeding 1mg/kg/day prednisone equivalent, [Appendix K](#)) are permitted for the treatment of cGVHD flare, but dose must be reduced back to the pre-randomization dose within 6 weeks. If the dose remains elevated for more than 6 weeks, this will be considered a belumosudil treatment failure. More than 2 episodes of cGVHD flare requiring increased corticosteroid therapy in the first 6 months of belumosudil treatment will also be considered a belumosudil treatment failure; this necessitates discontinuing from study drug.

Response assessments scheduled to occur during treatment of a cGVHD flare will be conducted as planned but will not be included in the primary efficacy analysis.

PD samples should be collected at time corticosteroid dose is increased. Refer to the Laboratory Manual for detailed instructions.

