11.2.1 Efficacy Decision Rules with Multiplicity Adjustment

The Hochberg procedure is the primary multiplicity adjustment method for inferential purposes for the primary endpoint ORR.

The inferential decision for primary endpoint of ORR is described below and shown in [Figure 2](#).

1. Calculate two-sided 99.5% confidence interval of ORR by using Clopper-Pearson (exact) method for both arms at interim analysis.
2. If the lower bounds of their 2-sided 99.5% confidence interval both are above 30%, then claim both arms are efficacious, and stop. Otherwise, go to Step 3.
3. If the lower bounds of their 2-sided 99.5% confidence interval both are below 30%, then cannot determine efficacy for either arm, and go to Step 5. Otherwise, go to Step 4.

[figure not shown]
4. Calculate 2-sided 99.75% confidence interval of ORR by using Clopper-Pearson (exact) method for treatment group with higher response rate. If its lower bound is above 30%, then claim this arm is efficacious, and go to step 6. Otherwise, cannot decide efficacy for both arms, and go to Step 5.
5. Use following Hochberg procedure for the 6-month primary efficacy analysis of ORR
 - a) Calculate 2-sided 95.5% confidence interval of ORR by using Clopper-Pearson (exact) method for both arms.
 - b) If the lower bounds of their 2-sided 95.5% confidence interval both are above 30%, then claim both arms are efficacious, and stop. Otherwise, go to Step 5c.
 - c) If the lower bounds of their 2-sided 95.5% confidence interval both are below 30%, then claim both arm are non-efficacious, and stop. Otherwise, go to Step 5d.
 - d) Calculate 2-sided 97.75% confidence interval of ORR by using Clopper-Pearson (exact) method for treatment group with higher response rate. If its lower bound is above 30%, then claim this arm is efficacious, and stop. Otherwise, claim both arms are non-efficacious, and stop.
6. At the 6-month primary analysis, calculate 2-sided 95.5% confidence interval (CI) of ORR by using Clopper-Pearson (exact) method for the treatment group with lower response rate at interim analysis. If its lower bound is above 30%, then claim this arm is efficacious, and stop. Otherwise, claim this arm is non-efficacious, and stop.

If one arm is discontinued in view of the prescribed stopping rules ([Section 10](#)), efficacy will only be assessed for the remaining arm without multiplicity adjustment.

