11.7 EFFICACY ANALYSES

11.7.1 Primary Efficacy Endpoint

The ORR is defined as the proportion of participants (from the mITT population) meeting the overall response criteria assessment of complete or partial responses at any post-baseline response assessment ([Section 6.3.2](#)).

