### **3.8.2.6 Corticosteroid dose**

Corticosteroid doses will be presented as mg/kg/day prednisone equivalent dose. Descriptive statistics for the mITT population, responder /nonresponder populations and subgroups defined by baseline corticosteroid dose level (upper and lower 50 percentiles) will be provided for:

- Systemic corticosteroid dose over time
- Change and % change from baseline (C1D1) to the greatest corticosteroid dose reduction during KD025 treatment period
- Number and % of subjects who reduced systemic corticosteroid dose during KD025 treatment period

- Number and % of subjects who ever discontinued systemic corticosteroid usage for over 28 days during KD025 treatment period

The above analyses will be censored on or after new systemic cGVHD treatment.

If subjects are not using prednisone as the systemic corticosteroid, then the prednisone dose equivalent will be determined according to following conversion ratios:

1 mg prednisone is equivalent to:

- 4mg Hydrocortisone
- 0.8mg Methylprednisolone
- 0.15mg Dexamethasone
- 1mg Prednisolone
- 0.8mg Triamcinolone

Transient increases in corticosteroid dosing (not exceeding 1mg/kg/day prednisone equivalent, are permitted for the treatment of cGVHD flare, but dose must be reduced back to the pre-randomization dose within 6 weeks. If the dose remains elevated for more than 6 weeks, this will be considered a KD025 treatment failure. More than 2 episodes of cGVHD flare requiring increased corticosteroid therapy in the first 6 months of KD025 treatment will also be considered a KD025 treatment failure.

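### SAP 3.8.1 counts a CR or PR at any post-baseline assessment and omits Protocol 5.8.1's exclusion of flare-time assessments from the primary analysis

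*SAP*

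**What the plan says.** **The exclusion.** Protocol 5.8.1 permits a transient corticosteroid increase to treat a cGVHD flare. It adds that response assessments scheduled "during treatment of a cGVHD flare will be conducted as planned but will not be included in the primary efficacy analysis".

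**The endpoint definitions.**
- Protocol 11.7.1 counts "complete or partial responses at any post-baseline response assessment", taken over the mITT population.
- SAP 3.8.1 counts participants "meeting the overall response criteria assessment of CR or PR at any post-baseline response assessment".
- The SAP 3.4 responder population is those who "achieved a partial or complete response at any post-baseline response assessment".

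None of the three mentions flares.

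**The handling rules in SAP 3.8.1.** There are two. A treated participant lost to follow-up without a response assessment is a non-responder. The other reads: "Any response on and after new systemic cGVHD treatment will be censored as non-response".

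**Flares elsewhere in the SAP.** SAP 3.8.2.6, on corticosteroid dose, restates the flare limits: transient increases of no more than 1 mg/kg/day "prednisone equivalent, are permitted for the treatment of cGVHD flare, but dose must be reduced back to the pre-randomization dose within 6 weeks". It also restates both treatment-failure conditions, but not the sentence about response assessments.

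**The concern.** Two rules decide who is a responder on the only endpoint that carries alpha, and they disagree for one kind of participant: someone whose only CR or PR is recorded while a flare is being treated. Protocol 5.8.1 sets that assessment aside; the SAP counts it.

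The SAP is the document that will be programmed. Protocol 11.5 sends all pre-specified analyses to it, and SAP section 1 says that it describes the data handling. Its authors did write exclusions out: the document history records that version 2.1 added the censoring rule for new systemic treatment.

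With the denominator fixed, the disagreement runs one way. Dropping an assessment can remove a responder but never create one, so ORR under the SAP is equal to or higher than ORR under Protocol 5.8.1.

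**Working it through.** **1. Does another SAP rule close the gap?** The only candidate is the rule for new systemic cGVHD treatment. Protocol 5.8 treats starting new systemic therapy as a treatment failure that ends study drug. Protocol 5.8.1 permits a transient steroid increase and makes it a failure only if it stays elevated beyond 6 weeks or if there are more than 2 such flares in the first 6 months. A permitted increase is therefore not clearly new systemic treatment, and a response during it stays in under SAP 3.8.1.

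**2. Is the denominator settled?** Yes. Protocol 11.7.1 takes the proportion from the mITT population. SAP 3.4 defines a non-responder as anyone in mITT who is not a responder. SAP 3.14 (Reporting of Numerical Values) makes the analysis population the default denominator. Under the exclusion, a participant with no other CR or PR stays in mITT as a non-responder.

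**3. Can a flare contain an assessment?** The first schedule in Protocol 3.1 assesses response on Day 1 of Cycles 2, 3, 4 and 5 (weeks 4, 8, 12 and 16).
- Largest gap with ±3-day windows: 28 + 3 + 3 = 34 days.
- Longest permitted increase: 6 × 7 = 42 days.
- Since 42 > 34, a full 42-day flare lying between weeks 4 and 16 contains at least one assessment.

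That is as far as the guarantee goes. A shorter flare may contain none. After Cycle 5 the gaps are 56 days. On the schedule for adolescents enrolled after Amendment 5 (Cycles 2, 3, 5, 7, 10, 13), gaps after Cycle 3 are 56 and then 84 days, so a 42-day flare can fall between visits.

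**4. Reproduce the plan's figures.** Inputs from Protocol 11.2 and SAP 3.1: n = 63 per arm, null ORR 30%, target 55%, dropout 10%, one-sided alpha 0.0225. Dropouts are counted as non-responders, so the effective ORR is 0.55 × 0.90 = 0.495.
- P(X ≥ 27 | n = 63, p = 0.495) = 88.1%, against a stated approximately 90%.
- Power for at least one arm under Hochberg = 97.2%, against 97% in Protocol Table 5b.

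**5. Thresholds.** These are for Protocol 11.2.1 step 5, with no claim at interim. The Clopper-Pearson lower bound must exceed 30%.

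| Interval | Responders of 63 | Lower bound | Result |
|---|---|---|---|
| 95.5% | 26 | 28.8% | fails |
| 95.5% | 27 | 30.2% | passes |
| 97.75% | 27 | 28.7% | fails |
| 97.75% | 28 | 30.1% | passes |

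An arm needs 27 if the other arm also passes at 95.5%. Otherwise step 5d applies ("Calculate 2-sided 97.75% confidence interval of ORR by using Clopper-Pearson (exact) method for treatment group with higher response rate") and it needs 28. One participant is 1/63 = 1.6 percentage points. The planning case gives 0.55 × 0.90 × 63 = 31.2, about 31 responders. Reversing it takes 31 − 26 = 5 flare-only responders if the other arm passes, or 31 − 27 = 4 if it does not.

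**6. Sensitivity only.** Suppose that both arms have an ORR of exactly 30% under Protocol 5.8.1, and that an assumed share q of the other participants respond only during a flare. The counted ORR is p = 0.30 + 0.70q, and the expected number of flare-only responders per arm is 63 × 0.70 × q. Both arms were enumerated exactly under step 5.

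| q (assumed) | Flare-only per arm | Claim, given arm | At least one claim |
|---|---|---|---|
| 0% | 0 | 1.1% | 2.1% |
| 2% | 0.9 | 2.1% | 4.0% |
| 5% | 2.2 | 4.8% | 9.1% |
| 10% | 4.4 | 15.0% | 26.0% |

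The documents supply no value of q.

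**The case against.** The best defence is that the two documents should be read together: Protocol 11.7.1 gives the general rule, 5.8.1 gives an exception, and the SAP inherits both. That reading of the protocol is reasonable. It does not rescue the SAP, which lists its own exceptions, restates the flare limits and leaves this one out. Nor is the gap explained by the SAP predating later amendments, since the protocol's change summaries list no later addition of the flare sentence.

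A second objection is that the affected group is narrow, because such a participant must have no CR or PR at any assessment outside flare treatment. This stands, and it is why the size may be zero.

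A third is that the primary analysis has probably been run. The Protocol Synopsis says that approval was based on data from this study, from which this is an inference. This also stands, and it changes the form of the remedy, not the finding. Analyses adding adolescent and Companion Study participants are still planned in Protocol 11.

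Three stronger readings are tempting, and the documents do not support them:
- **That the denominator is open.** A reader might infer from the SAP 3.14 missing-data default that excluded participants leave the percentage. That default yields where the plan specifies otherwise, and step 2 shows that it does.
- **That ORR is inflated.** No flare rate or flare-only response rate is given. The table in step 6 shows sensitivity under assumed shares, with both arms exactly at the null.
- **That overlap is bound to occur.** Step 3 shows that this holds only for a full 42-day flare between weeks 4 and 16 on the first schedule.

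**Conclusion.** The point holds. As written, SAP 3.8.1 and the SAP 3.4 responder population give responder status to a participant whom Protocol 5.8.1 would not count, and Protocol 11.7.1 does not carry the exception either. The direction is certain with the mITT denominator fixed: ORR under the SAP is equal to or above ORR under 5.8.1. The size cannot be derived from the documents and is zero if every participant with a flare-time response also responds outside a flare. At a threshold of 27/63 or 28/63 one participant decides the claim; from the planning case it takes 4 or 5. These counts assume 63 per arm and no claim at interim. Because the conflict affects the only alpha-controlled endpoint and is cheap to remove, it should be settled before any further ORR analysis.

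**What to change.** Reconcile Protocol 5.8.1, Protocol 11.7.1 and SAP 3.8.1. If the 5.8.1 exclusion stands:

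1. Add to SAP 3.8.1, with a cross-reference in Protocol 11.7.1: *Response assessments made during treatment of a cGVHD flare do not count toward best overall response in the primary ORR. Participants remain in the mITT denominator and evaluable at all other assessments, and are non-responders if they have no CR or PR outside flare treatment.*
2. Define the flare-treatment window for analysis from recorded corticosteroid dosing dates. Protocol 5.8.1 allows tapering ("Corticosteroids may be tapered at the discretion of the Investigator after" at least 2 weeks of study drug), so say how a flare increase is identified in a participant already below the pre-randomization dose. The sponsor should pre-specify how a missing end date is handled; the documents give no rule, and leaving the window open indefinitely could discard valid later responses.
3. State that the SAP 3.4 responder population follows the same rule, and apply it in the additional adolescent and Companion Study analyses.
4. Report ORR with flare-time assessments included as a sensitivity analysis.
5. If the primary analysis has already been run, report ORR under the 5.8.1 rule beside the reported ORR, labelled as a reconciliation.

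**Cost:** one SAP paragraph, one protocol cross-reference, a little programming and possibly a review of steroid records to identify flare periods. The primary ORR may be slightly lower.
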